## **6.3. Secondary Immunogenicity Endpoints**

Proportion (or percentage) of participants with demonstrated seropositivity for mumps at 56 days post-vaccination. Seropositivity will be defined as an optical density ratio  $\geq$  1.10 using a commercial ELISA manufactured by Zeus Scientific, Inc., Branchburg, NJ.

- Geometric mean concentration (GMC) for anti-measles neutralizing antibody concentration at 56 days post-vaccination
- GMC for anti-rubella IgG antibody concentration at 56 days post-vaccination
- Seroconversion rates for measles at 56 days post-vaccination, defined as the proportion of participants with a change in serostatus from negative to positive 56 days after vaccination or a four-fold rise in concentration 56 days after vaccination if seropositive for measles at baseline
- Seroconversion rates for mumps at 56 days post-vaccination, defined as the proportion of participants with a change in serostatus from negative to positive 56 days after vaccination
- Seroconversion rates for rubella at 56 days post-vaccination, defined as the proportion of participants with a change in serostatus from negative to positive 56 days after vaccination or a four-fold rise in concentration 56 days after vaccination if seropositive for rubella at baseline.
- Proportion (or percentage) of participants with demonstrated seropositivity for JE at 28 days post-vaccination with CD-JEV. Seropositivity will be defined as a JE serum neutralizing antibody titer of ≥ 1:10, as measured by JE PRNT-50.
- Geometric mean titer (GMT) for serum neutralizing antibody titer to JE virus at 28 days post-vaccination

## 6.4. Analysis of Secondary Immunogenicity Endpoints

- Proportions (or percentage) of participants with seropositivity for mumps at 56 days post-vaccination between Group 1 and Group 2 will be compared using a non-inferiority test. Non-inferiority of Group 1 to Group 2 in terms of seropositivity for mumps will be demonstrated if the lower limit of the two-sided 95% CI for the difference of seropositivity rates between the two groups (concurrent administration minus separate administration) at 56 days post-vaccination is > -10%. The 95% CI will be calculated using the Farrington-Manning method. The proportion of participants with seropositivity for mumps at 56 days post-vaccination will be presented with exact 95% CI by study group.
- The ratio of anti-measles GMCs between the two groups (ratio of concurrent administration to separate administration) along with 95% CI of the ratio at 56 das post-vaccination will be obtained using analysis of covariance (ANCOVA) approach that includes log10-transformed antibody concentration as the dependent variable and the treatment group as the explanatory variable adjusted for log10-transformed baseline antibody concentration. The anti-measles GMC with its 95% CI will be provided by study group. The same approach will be applied to anti-rubella GMCs.
- The 95% CI of the difference in anti-measles seroconversion rates between the two groups (concurrent administration minus separate administration) at 56 days post-vaccination will be calculated using the Farrington-Manning method. The

seroconversion rate will be presented with exact 95% CI by study group. The sample approach will be employed to anti-mumps and anti-rubella seroconversion rates.

- The 95% CI of the difference in proportion (or percentage) of participants with seropositivity for JE between the two groups (concurrent administration minus separate administration) at 28 days post-vaccination with CD-JEV will be calculated using the Farrington-Manning method. The JE seropositivity rate will be calculated with exact 95% CI by study group.
- The ratio of anti-JE GMTs between the two groups (ratio of concurrent administration to separate administration) along with 95% CI of the ratio at 28 days post-vaccination with CD-JEV will be obtained using analysis of covariance (ANCOVA) approach that includes log10-transformed antibody titer as the dependent variable and the treatment group as the explanatory variable adjusted for log10-transformed baseline antibody titer. The age prior to vaccination with CD-JEV will be evaluated for inclusion as covariate in ANCOVA model. The anti-JE GMT with its 95% CI will be summarized by study group.

#### **6.5. Exploratory Analyses**

#### 6.5.1. Immunogenicity Endpoints of Exploratory Analysis

- Proportion (or percentage) of participants with presence of anti-dengue IgG as measured by ELISA prior to vaccination with CD-JEV.
- Proportion (or percentage) of participants with anti-dengue serotype 1-, 2-, 3-, and 4-specific serum neutralizing antibody titer of ≥ 1:10 as measured by dengue PRNT-50 prior to vaccination with CD-JEV.

#### 6.5.2. Exploratory Immunogenicity Analysis

The proportions along with 95% exact CI for anti-dengue antibody response will be calculated by study group.

To assess the effect of pre-existing anti-dengue antibody prior to vaccination with CD-JEV on CD-JEV immunogenicity 28 days following immunization, a two-way cross tabulation of anti-dengue antibody status (non-presence/presence, negative/positive) prior to vaccination with CD-JEV and anti-JE antibody response (negative/positive) 28 days post-vaccination will be provided. The association between pre-existing anti-dengue antibody and anti-JE antibody response post-vaccination will be tested by Fisher's Exact Test.

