**Table 2. Seropositivity rates and anti-measles IgG geometric mean concentrations and anti-JE geometric mean titers in Philippine infants vaccinated with JE and measles vaccines.**

		Group 1 (CD-JEV then MV) (N=88)		Group 2 (concomitant) (N=219)		Group 3 (MV then CD-JEV) (N=178)	
		% seropositive (95% CI)	GMC/GMT (95% CI)	% seropositive (95% CI)	GMC/GMT (95% CI)	% seropositive (95% CI)	GMC/GMT (95% CI)
Measles vaccine response (anti-measles IgG)	Day 0	1.1 (0.0-6.2)	12.8 a (10.2-16.2)	0.0 (0.0-1.7)	7.4 (6.3-8.8)	0.0 (0.0-2.1)	7.0 (5.8-8.5)
	Day 28	88.6 (80.1-94.4)	318.9 (273.0-372.6)	91.8 (87.3-95.1)	301.9 (269.0-338.9)	86.5 (80.6-91.2)	262.5 (222.2-310.2)
JE vaccine response (anti-JE neutralizing antibody)	Day 0	3.4 (0.7-9.6)	5.7 (4.9-6.5)	5.4 (2.8-9.3)	5.7 (5.2-6.1)	6.1 (3.1-10.7)	5.9 (5.3-6.6)
	Day 28	92.1 (84.3-96.7)	202.8 (140.5-292.9)	90.5 (85.9-94.1)	155.0 (123.5-194.5)	90.6 (85.3-94.4)	139.4 (109.5-177.5)
	Year 1	90.2 (82.2-95.4)	106.8 (71.5-159.4)	84.0 (78.3-88.6)	80.7 (62.4-104.3)	85.9 (80.5-90.3)	74.9 (59.2-94.9)
	Year 2	81.7 (72.4-89.0)	68.8 (47.3-100.1)	83.0 (77.3-87.8)	61.6 (49.1-77.4)	81.7 (75.8-86.6)	70.1 (54.6-90.1)
	Year 3	79.6 (70.0-87.2)	49.9 (36.5-68.3)	81.9 (75.9-86.8)	45.7 (37.2-56.3)	82.6 (76.8-87.4)	59.3 (47.1-74.8)

CD-JEV: live, attenuated Japanese encephalitis SA 14-14-2 vaccine; MV: measles vaccine; N: number of infants in the per protocol analysis; CI: confidence interval; GMC: milli International Units per milliliter (mIU/mL), seroprotection defined as  $\geq 120$  mIU/mL; GMT: geometric mean titer, seroprotection defined as  $\geq 1:10$ .

a Although measles GMC/GMT at baseline were higher in Group 1, the GMC/GMT 28 days after vaccination were not significantly different.

Seroresponse rates to CD-JEV may not be equal in all pediatric populations. A lot-to-lot consistency study conducted in 2012 among 10-month-old Bangladeshi infants in a rural area with a low incidence of JE demonstrated a seropositivity rate of only 82.3% (95% CI 79.0-85.2%) following a single vaccine dose. The reasons for this lower response rate are unclear, but may be related to the high rates of malnutrition found in the population or other population-specific causes. Nevertheless, these findings highlight the value of assessing the performance of the vaccine in other high-risk populations.

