### **8.2.2. Serum Assays**

#### **8.2.2.1. Anti-Japanese Encephalitis Immunogenicity Testing**

JE vaccine immunogenicity will be assessed by measurement of serum anti-JE neutralizing antibody. Testing will be performed at the Department of Virology, Armed Forces Research Institute of Medical Sciences in Bangkok, Thailand. A 50% PRNT will be used to measure neutralizing antibodies for JE. Seroprotection will be defined as a serum JE PRNT titer of  $\geq 1:10$ .

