## 2.1.3. Exploratory Objectives

To assess the effect of pre-existing anti-dengue antibody on CD-JEV immunogenicity. Pre-existing anti-dengue antibody will be measured first by the presence of anti-dengue IgG in ELISA and secondly by anti-dengue serum neutralizing antibody titer of  $\geq 1:10$  as measured by dengue PRNT-50.

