#### 3.4. Data Handling Conventions and Transformations

For Group 1, baseline antibodies to measles, rubella, mumps, JE, and dengue will be tested on Day 0. For Group 2, baseline antibodies to measles, rubella, and mumps will be assessed on Day 0 and baseline antibodies to JE and dengue will be tested on Day 56.

The antibody concentrations/titers to measles, rubella, JE, and dengue will be transformed using log10 transformation. Data will be back-transformed to the original scale for presentation.

Numerical numbers will be presented to one decimal place if applicable.

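### The dengue objective judges JE response only as negative or positive at 1:10, so about two-fold shifts in CD-JEV titre, above all increases, would often go undetected

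*SAP*

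**What the plan says.** The objective is broad: "To assess the effect of pre-existing anti-dengue antibody on CD-JEV immunogenicity" (SAP 2.1.3; Protocol 3.1.3 matches it). Protocol 11.5.3 asks for any association between the baseline dengue response and the Day 28 anti-JE response. It names no method and does not limit the JE response to two categories.

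SAP 6.5.2 narrows this. Dengue antibody status before CD-JEV is tabulated against JE response in two categories: "anti-JE antibody response (negative/positive) 28 days post-vaccination will be provided". One test is named: "The association between pre-existing anti-dengue antibody and anti-JE antibody response post-vaccination will be tested by" Fisher's exact test. No comparison of JE titre by dengue status appears anywhere in the SAP, and dengue status is not among the covariates in SAP 3.2.

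The titre itself is available and in use:
- SAP 6.3 lists it as an endpoint: "Geometric mean titer (GMT) for serum neutralizing antibody titer to JE virus at 28 days post-vaccination".
- SAP 3.4 puts it on the log10 scale.
- SAP 6.4 models it between study groups by ANCOVA, with the log10-"transformed antibody titer as the dependent variable and the treatment group as the explanatory variable", adjusted for baseline titre.

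The cut-off carries a meaning in the protocol. Section 8.2.2.1 states: "Seroprotection will be defined as a serum JE PRNT titer of" at least 1:10.

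**The concern.** When about nine infants in ten are already positive, a two-category outcome says little about the level of response. Protocol Table 2 gives Day 28 GMTs of 139.4, 155.0 and 202.8 in the three groups, that is, 14 to 20 times the cut-off of 10. An infant near the middle of that distribution can gain or lose several-fold in titre and stay in the same cell. Increases are hit hardest, because the rate has less than 10 percentage points left to rise.

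What is at stake is how a non-significant Fisher result can be read. It would be weak evidence that dengue antibody leaves CD-JEV immunogenicity unchanged, although data that answer the question better will already be in the database.

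**Working it through.** **The plan's own figure.** The documents state no power for the dengue objective, only for the co-primary endpoints. That figure reproduces. The Farrington-Manning sample size for rubella (90% in both groups, margin 10%, one-sided 2.5%, power 95%) is 250.7, so 251 evaluable per group, and 251/0.80 = 314 enrolled per group. If the same 20% non-evaluable rate is assumed for JE, 2 × 251 = 502 infants enter the dengue analysis.

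**Inputs from Protocol Table 2** (Day 28, concomitant group, N = 219): 90.5% positive; GMT 155.0 (95% CI 123.5-194.5).

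**Spread of the titre.** From the CI: SD = (log10 194.5 − log10 123.5) / (2 × t) × √219, with t = 1.971 on 218 df. That is 0.1973/3.942 × 14.80 = 0.74. From the positivity rate: SD = (log10 155 − 1)/z(0.905) = 1.190/1.311 = 0.91. The two differ, so GMT, CI and percentage positive do not fit a single normal curve. Both ends are carried below: SD 0.91 (90.5% positive) and SD 0.745 (94.5% positive).

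**What a two-fold shift does to the positivity rate.** P(positive) = Φ[(log10 GMT − 1)/SD].

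| GMT | SD 0.91 | SD 0.745 |
|---|---|---|
| 155 (no shift) | 90.5% | 94.5% |
| 77.5 (halved) | 83.6% | 88.4% |
| 310 (doubled) | 95.0% | 97.7% |

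**Power.** Simulation of 2,000 trials per setting: 502 infants, two-sided 5%, titres below 10 set to 5. Fisher's exact test on negative/positive is compared with a Welch t-test on log10 titre. Dengue prevalence is assumed at 10%, 30% and 50%. Ranges span the two SDs.

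| Shift in dengue-positive infants | Prevalence | Binary | log10 titre |
|---|---|---|---|
| Two-fold fall | 10% | 30-39% | 61-76% |
| | 30% | 57-60% | 92-99% |
| | 50% | 60-64% | 96-99.5% |
| Two-fold rise | 10% | 1-12% | 58-76% |
| | 30% | 35-36% | 92-99% |
| | 50% | 37-44% | 95-99.5% |
| Three-fold fall | 10% | 67-75% | 93-99% |
| | 30% | 94-97% | 100% |
| | 50% | 96-99% | 100% |

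For a 1.5-fold shift either way at 30-50% prevalence, the binary test has 14-22% and the titre 49-75%. A repeat with a different random seed agreed within simulation error.

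**Why the rise can be almost invisible.** At 10% prevalence there are 50 dengue-positive and 452 dengue-negative infants. At 94.5% positivity about 25 of the 452 are JE-negative (452 × 0.055 = 24.9). Even if none of the 50 were JE-negative, Fisher's two-sided p for 0/50 against 25/452 is 0.16.

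**The case against.** The strongest reply is that 1:10 is the only threshold to which the documents attach meaning. Protocol 8.2.2.1 and the footnote to Table 2 call it seroprotection, and the binary table measures exactly whether dengue antibody costs infants that status. An infant who falls from 200 to 100 is still seroprotected by this definition. This stands, and it is why the table should stay.

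A reader might infer that clinically relevant changes in CD-JEV response would be missed. The documents do not support that:
- No passage defines a clinically relevant titre shift.
- A three-fold fall, which takes positivity from 90.5% to about 78% (SD 0.91), is found with 94-99% power at 30-50% prevalence. Only at 10% does power drop to 67-75%.

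The inputs are also uncertain. Dengue prevalence in these infants is not given. The 20% non-evaluable rate is stated for the 56-day MMR endpoints. Protocol 2.1.6 reports only 82.3% JE-positive in a Bangladeshi infant population, where the ceiling would press less. This is a reason to give ranges, but it does not reverse the comparison. In a wider simulation (500 infants, 25-250 dengue-positive, baseline positivity about 82-95%) the titre had more power for every two-fold shift: 37-99% against 21-88% for a fall, and 32-99% against 0-75% for a rise. The low ends show that with very few dengue-positive infants neither analysis is informative.

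Finally, the objective is exploratory and unpowered, no passage says that a non-significant result will be read as no effect, and a titre summary could still be added at reporting. All true. They limit the weight of the point, but a comparison added at reporting would not be pre-specified.

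**Conclusion.** The point holds as a minor one. SAP 6.5.2 answers a question about immunogenicity with its coarsest JE measure, while the titre is already an endpoint and already modelled. Under the stated assumptions, two-fold shifts would often go undetected: binary power is 30-64% for a fall and 1-44% for a rise, against 61-99.5% and 58-99.5% on the titre. The exact values depend on assumed dengue prevalence, JE-evaluable number, the value given to titres below 1:10 and a log-normal shape. The direction of the comparison was the same in every two-fold setting tried.

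The conclusion goes no further than that. Large falls are usually detected unless dengue positivity is rare, loss of seroprotection is captured by the planned table, and no primary or secondary conclusion is affected.

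**What to change.** In SAP 6.5.2, keep the negative/positive table and Fisher's exact test, labelled as the seroprotection result. Add a pre-specified comparison of log10 Day 28 anti-JE titre by dengue antibody status. Report it as a GMT ratio (antibody present versus absent) with 95% CI, obtained by adding dengue status to the anti-JE ANCOVA of SAP 6.4, with study group and log10 baseline JE titre as covariates. State the value assigned to titres below 1:10.

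The cost is a few lines of SAP text, one extra model and one extra table, on data already collected. No samples, assays or visits are added.

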### **11.5.3. Exploratory Analyses**

Post-vaccination serologic responses will be analyzed for any association between the baseline anti-dengue antibody response and the anti-JE antibody response 28 days after vaccination with CD-JEV.

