## 2.1.2. Secondary Objectives

1. To demonstrate the non-inferiority of MMR vaccination in terms of mumps immunogenicity when administered to infants 9 months of age concomitantly with CD-JEV compared to administration alone, as assessed by the rate of seropositivity 56 days after vaccination.

Mumps vaccine immunogenicity will be evaluated by the presence of serum antimumps IgG antibody. Seropositivity will be defined as an OD ratio  $\geq$ 1.10 using a commercial ELISA manufactured by Zeus Scientific, Inc., Branchburg, NJ.

- 2. To evaluate geometric mean concentration (GMC) for serum anti-measles neutralizing antibody concentration and anti-rubella IgG GMC at 56 days post-vaccination, comparing when MMR vaccine is co-administered with CD-JEV to when MMR vaccine is given alone.
- 3. To evaluate anti-measles, anti-mumps, and anti-rubella seroconversion rates 56 days after vaccination, comparing when MMR vaccine is co-administered with CD-JEV to when MMR vaccine is given alone. For participants seronegative at baseline, seroconversion will be defined as a change to seropositive status (as defined above). For participants seropositive for measles or rubella at baseline, seroconversion will be defined as a four-fold rise in concentration.
- 4. To compare the anti-JE seropositivity rate 28 days after CD-JEV vaccination administered concurrently with MMR vaccine to CD-JEV administered alone. Anti-JE seropositivity will be defined as an anti-JE serum neutralizing antibody titer of ≥1:10, as measured by JE PRNT-50.
- 5. To describe geometric mean titer (GMT) for anti-JE neutralizing antibody titer 28 days after CD-JEV vaccination when MMR vaccine is co-administered compared to when CD-JEV is administered alone.
- 6. To describe the safety profiles of CD-JEV and MMR vaccine when given concurrently and separately, as assessed by immediate reactions occurring within 30 minutes, solicited injection site and systemic adverse reactions occurring

within 14 days, unsolicited adverse events (AEs) occurring within 28 days, and SAEs throughout the course of the study.

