Baseline serology will be tested for antibodies to JE, measles, mumps, rubella, and dengue virus. Antibody responses to CD-JEV will be tested 28 (+7) days after vaccination, while antibody responses to the first dose of MMR will be tested 56 (+7) days after vaccination. Specifically, antibodies to measles, mumps, and rubella will be tested on Day 0 and Day 56 (+7) for both Group 1 and Group 2; antibodies to JE will be assessed on Day 0 and Day 28 (+7) for Group 1 and on Day 56 (+7) and Day 84 (+7) for Group 2; antibodies to dengue will be tested on Day 0 for Group 1 and on Day 56 (+7) for Group 2. All laboratory testing will be conducted in a blinded fashion.

Except for a screening visit which may occur on Day 0 or before, a total of 9 visits is planned for participants in Group 1 and a total of 11 visits is planned for participants in Group 2. The duration of study participation for each participant is 4 months. The duration of the study is expected to be 7 to 8 months, dependent upon the duration of enrollment period. The schedule of study visits and activities is presented in Table 1 below.

The study will be conducted at Putatan Health Center and Bayanan Health Center located within the study area of the Research Institute for Tropical Medicine, Manila, Philippines.

	Group 1									
	efore D0	D0	D2 (+3)	D14 (+3)	D28 (+7)	D56 (+7)	D84 (+7)	D86 (+3)	D98 (+3)	D112 (+7)
Obtain informed consent	x									
Collect baseline demographic information		х								
Collect/review medical history		х								
Perform physical examination		х		x	x	х	х		х	x
Check/confirm inclusion/exclusion criteria		х								
Collect serum for serology testing		х			x	х				
Administer dose of MMR		х					х			
Administer dose of CD-JEV		х								
Observe for immediate reactions for 30 minutes		х					х			
Provide diary card to parent/guardian		х					х			
Call participant to inquire about child's well-being			x					х		
Collect diary card and review reported adverse events				x					х	
Record reported adverse events		х			x	x	х			x
Record reported serious adverse events		х	x	x	x	x	х	х	х	x
Exit participant from study										х

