## **3.2.** Adjustment for Covariates

No adjustments for covariates are planned for the primary analysis. For the comparison of ant-measles and anti-rubella GMCs and anti-JE GMT between treatment groups, baseline antibody concentration/titer will be included in the analysis as covariate. In addition, age prior to vaccination with CD-JEV will be evaluated for inclusion as covariate for the comparison of anti-JE GMT between study groups.

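### The dengue–JE association tests in SAP 6.5.2, read naturally, pool the two study groups and can be confounded by group; a test stratified by group removes this at almost no cost

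*SAP*

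**What the plan says.** SAP 6.5.2 has three steps. It first summarises dengue status: "The proportions along with 95% exact CI for anti-dengue antibody response will be calculated by study group". It then provides "a two-way cross tabulation of anti-dengue antibody status (non-presence/presence, negative/positive) prior to vaccination with CD-JEV" against JE response (negative or positive) 28 days after CD-JEV. Finally it names the test: "The association between pre-existing anti-dengue antibody and anti-JE antibody response post-vaccination will be tested by Fisher's Exact Test". Study group is mentioned in the first step only.

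SAP 6.5.1 defines several dengue statuses: IgG by ELISA, and neutralizing antibody to each of serotypes 1 to 4. More than one table and test is therefore implied.

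On timing, SAP 2.2 says "antibodies to dengue will be tested on Day 0 for Group 1 and on Day 56 (+7) for Group 2", and SAP 3.4 says that for Group 2 "baseline antibodies to JE and dengue will be tested on Day 56". Protocol 11.5.3 asks only for "any association between the baseline anti-dengue antibody response and the anti-JE antibody response 28 days after vaccination" and names no method.

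Two other places bear on the point. A secondary objective (SAP 2.1.2) is "To compare the anti-JE seropositivity rate 28 days after CD-JEV vaccination administered concurrently with MMR vaccine to CD-JEV administered alone". SAP 3.2 says that "age prior to vaccination with CD-JEV will be evaluated for inclusion as covariate for the comparison of anti-JE GMT between study groups", but carries no covariate or stratification into the dengue analysis.

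**The concern.** A pooled two-way table is safe only if study group is unrelated to at least one of its margins. Randomization does not secure that here.

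- **Dengue status.** It is read at about 9 months of age in Group 1 and about 11 months in Group 2. Randomization balances the groups at Day 0, not dengue prevalence at two different ages.
- **JE response.** The groups differ in co-administration, in age at CD-JEV and in prior MMR. Whether response differs is one of the trial's questions.

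If both margins differ by group, the pooled odds ratio mixes the group difference with any dengue effect. The exploratory objective could then report a dengue effect that neither group shows, or miss one that both show.

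**Working it through.** **Inputs from the documents**

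- 314 enrolled per group, with about 20% non-evaluable (SAP 2.3).
- Historical Day 28 JE seropositivity in Philippine infants: 90.5% with measles vaccine given concomitantly, 90.6% with measles vaccine first (Protocol Table 2).
- A lower JE rate of 82.3% in another population (Protocol 2.1.6).
- Two-sided testing (SAP 3).

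**Assumptions**

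- Dengue prevalence in each group. The documents give none.
- JE gaps other than the historical pair.
- A 5% level. None is stated for this test.
- 251 evaluable per group. The 20% rate is stated for MMR at Day 56 and is borrowed here.

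**The plan's own figure.** A Farrington-Manning score calculation with rates 90% vs 90%, margin 10%, one-sided 2.5% and 95% power gives 251 evaluable per group. 251 / 0.80 = 313.75, so 314 per group, as stated. The dengue analysis has no sample size of its own.

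**Pooled odds ratio when dengue has no effect within either group.** Let d1, d2 be the dengue-positive proportions and j1, j2 the JE response rates in Groups 1 and 2, with equal group sizes:

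- JE response in dengue-positives: (d1·j1 + d2·j2) / (d1 + d2)
- JE response in dengue-negatives: ((1−d1)·j1 + (1−d2)·j2) / (2 − d1 − d2)

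The true odds ratio is 1.

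- *Dengue 50/30, JE 85/95.* Positives: (0.425 + 0.285) / 0.80 = 0.8875. Negatives: (0.425 + 0.665) / 1.20 = 0.9083. Odds ratio 7.89 / 9.91 = 0.80.
- *Dengue 60/20, JE 85/95.* Positives: (0.51 + 0.19) / 0.80 = 0.875. Negatives: (0.34 + 0.76) / 1.20 = 0.9167. Odds ratio 7 / 11 = 0.64.
- *Direction reversed, dengue 30/50, JE 85/95.* Positives: (0.255 + 0.475) / 0.80 = 0.9125. Negatives: (0.595 + 0.475) / 1.20 = 0.8917. Odds ratio 10.43 / 8.23 = 1.27. The bias can go either way.

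**Simulated type I error of the pooled Fisher test** (4,000 trials per scenario, 251 per group, no within-group effect)

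| Dengue, G1/G2 (%) | JE, G1/G2 (%) | Pooled odds ratio | Pooled Fisher |
|---|---|---|---|
| 20/20 | 85/95 | 1.00 | 3.4% |
| 80/20 | 90.5/90.6 | 0.99 | 4.2% |
| 30/20 | 88/93 | 0.93 | 4.6% |
| 40/20 | 88/93 | 0.87 | 6.8% |
| 50/30 | 85/95 | 0.80 | about 10% |
| 40/20 | 85/95 | 0.78 | 12.4% |
| 60/20 | 82.3/90.5 | 0.75 | 18.0% |
| 60/20 | 85/95 | 0.64 | about 30% |

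A Cochran-Mantel-Haenszel test stratified by group stayed between 4.1% and 6.2% throughout.

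**Power.** With equal dengue prevalence in the groups and a within-group odds ratio of 0.4, the stratified test had 91.6% power against 90.1% for the pooled Fisher test. The small advantage partly reflects the conservatism of Fisher's test. The point is that stratifying loses nothing.

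**The case against.** **Pooling is inferred.** The SAP does not say that the groups are pooled. This is correct. The inference rests on the table having two dimensions and on study group being named only for the dengue proportions. If tables by group were intended, the SAP does not say so and gives no combined test. The same amendment serves either reading.

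**The documents' own JE rates show no distortion.** At 90.5% vs 90.6% the pooled test is sound even with dengue at 80% vs 20%. A reader might infer from the design that the test *is* confounded, but the documents do not support that, because they do not establish a difference in either margin. Equally, the historical rates do not settle the matter. They come from measles vaccine, not MMR. Protocol 2.2 says that no data exist on CD-JEV with MMR, and cites a yellow fever–MMR study suggesting interference as a reason for the trial.

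**The large figures need large gaps.** This also stands. Nothing in the documents supports a 20- to 40-point dengue difference over two months, so the 30% figure is an extreme case and not a forecast.

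**The timing is deliberate.** A reader might take Day 0 against Day 56 as a measurement error. It is not: both samples immediately precede CD-JEV, as the objective requires. The gap is in age and MMR history, not in time relative to CD-JEV.

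**The sample size is borrowed.** The 251 does not come from the JE per-protocol set. The Protocol's Schedule of Serum Testing makes dengue PRNT conditional, so the serotype tables may be smaller.

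**Readers could see the problem.** Dengue proportions and JE seropositivity are both reported by group, so a difference in both would be visible. That would flag the bias but not correct the test.

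**Conclusion.** The concern holds as a possible confounding, not a demonstrated one. Bias arises only if dengue prevalence and JE response both differ by group. On assumed rates with 251 per group, the pooled type I error runs from no inflation (about 4% to 5% at the historical JE rates or with small gaps), through about 10%, to about 30% in an extreme case. The stratified test stays near 5%. These figures show a range and predict nothing about this trial. The issue applies to each dengue status tested. It is minor: no primary or secondary conclusion depends on it.

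**What to change.** Amend SAP 6.5.2 so that, for each dengue status (ELISA IgG and each serotype-specific PRNT result):

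1. the dengue-by-JE table is shown separately for Group 1 and Group 2;
2. the association is tested with study group as stratum, by Cochran-Mantel-Haenszel or, where cells are small, its exact version;
3. a common odds ratio with 95% CI is reported.

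The cost is a sentence or two in the SAP and a small programming change. No new samples, visits or participants are needed, and the power check showed no loss. It should be settled before the first of the two final analyses (SAP 3.7), which reports the exploratory objective.
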